8.3 Study Sponsor Fax Notification by Investigator

Of reportable AEs, certain events must be faxed to Stryker within 24 hours for timely notification:

- Events which meet the definition of serious
 - This does not include elective procedures, as these events are not reportable according to this study protocol.
- Events which are deemed to be “related to” or “uncertain” in regard to relation to the device

An AE CRF must be completed by the investigator and faxed to Stryker within 24 hours. The investigator will keep a copy of this AE CRF on file at the study center and submit the hard copy as per CRF data submission procedures. Report SAEs to one of the following study personnel:

[name]
[contact]
[contact]
[contact]

[name]
[contact]
[contact]
[contact]

At the time of the initial report, the following information should be provided:

• Subject number• A description of the event• Date of onset• Current status	
• Whether study treatment was discontinued• Investigator assessment of the association between the event and the study treatment
--	---

8.3.1 Ethics Committee/Institutional Review Board Notification by Investigator

Reports of AEs (including follow-up information) must be submitted to the Ethics Committee (EC) or Institutional Review Board (IRB) according to their specific requirements. Copies of each report and documentation of EC/IRB notification and receipt will be kept with the investigator's study files.

CONFIDENTIAL

8.4 Recording of Adverse Events

All protocol defined AEs occurring during the study period must be recorded; this includes events that occur between visit intervals. The clinical course of each event should be followed until resolution or stabilization.

8.5 Medical Monitoring

It is the responsibility of the investigator to oversee the safety of the study at his/her center. This safety monitoring will include careful assessment and appropriate reporting of AEs, as previously noted. Stryker will conduct formal investigations via the Product Surveillance Department of those AEs which are submitted through our PER System.

9 Statistical Plan

9.1 Efficacy

9.1.1 Primary Efficacy Parameters

The primary efficacy parameter will be femoral stem/neck construct revision/removal for any reason.

9.1.2 Secondary Efficacy Parameters

The secondary efficacy parameters include:

- Biomechanical measurement change from preoperative plan at 6-week visit
- HHS at each visit
- SF-12 scores at each visit
- LEAS at each visit

9.1.3 Primary Efficacy Hypothesis

The primary hypothesis to be tested will be that the proportion of cases without femoral stem/neck construct revision/removal is no worse for patients with the Rejuvenate® Modular Hip System than for cases with the Secur-Fit™ HA monolithic femoral stem at 5 years. A non-inferiority comparison with a one-sided alpha set at 0.05, power of 80% and delta of 7% will be performed. That is, the following hypothesis will be tested:

$$H_0: P1 < P2 - \delta \quad \text{vs.} \quad H_a: P1 > P2 - \delta$$

CONFIDENTIAL

where P1 and P2 are the proportions of cases without femoral stem/neck construct revision/removal for any reason for the Rejuvenate[®] Modular Hip System group and the Secur-Fit[™] HA monolithic femoral stem control group, respectively and $\delta=7\%$.

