Statistical Methodology	
Primary:
 
The 90% confidence interval around the difference in success rate (Rejuvenate® Modular Hip System – Secur-Fit™ HA monolithic femoral stem) will be computed at 5 years postoperative. For the non-inferiority comparison, the lower bound of this 90% confidence interval will be compared with -5%.
 
Secondary:
 
• A t-test or Wilcoxon test will be used to compare the postoperative biomechanical measurements to a preoperative plan.• Independent group t-tests will also compare HHS, SF-12 and LEAS at applicable time points between the Rejuvenate® Modular Hip System and Secur-Fit™ HA monolithic femoral stem groups. In addition, a paired t-test will compare the results preoperatively with each postoperative evaluation within the Rejuvenate® Modular Hip System group.• The adverse event (AE) rates and 95% confidence intervals will be presented within the Rejuvenate® Modular Hip System group. A Fisher's exact test will be used to compare the AE rates between the Rejuvenate® Modular Hip System and the Secur-Fit™ HA groups, if appropriate.• Radiographic data will be summarized in table format.
--------------------------------	---

CONFIDENTIAL

Evaluation Schedule

Evaluation	Preop X-rays (-1 yr) CRFs (-4 mos)	Intraop	6 weeks (± 3 wks)	1 year (± 2 mos)	2 years (± 2 mos)	3 years (± 3 mos)	4 years (± 4 mos)	5 years (± 4 mos)	6 years (± 4 mos)	7 years (± 4 mos)	8 years (± 4 mos)	9 years (± 4 mos)	10 years (± 4 mos)
Inclusion/ Exclusion	X												
Demographics & Medical History	X												
Preoperative Functional Evaluation	X												
Preoperative Biomechanical Measurements	X												
Surgical Details		X											
Postoperative Functional Evaluation			X	X	X	X	X	X		Optional			Optional
Postoperative Biomechanical Measurements			X										
SF-12	X		X	X	X	X	X	X		Optional			Optional
LEAS	X		X	X	X	X	X	X		Optional			Optional
Radiographs: Anteroposterior (AP) pelvis, AP femur, lateral	X		X	X	X	X	X	X		Optional			Optional
Follow-up Questionnaire									X	X	X	X	X

Functional Evaluation: The Functional Evaluations include the HHS, a subjective outcomes tool completed by the investigator that measures function, pain and motion.

SF-12: The SF-12 is a 12 item patient questionnaire that evaluates general health and well being.

LEAS: The LEAS is a self-administered patient evaluation designed to reflect patient activity.

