9.1.4 Primary Efficacy Analysis

A case success is defined as no incidence of femoral stem/neck construct revision/removal. The 90% confidence interval around the difference in success rate (Rejuvenate[®] Modular Hip System – Secur-Fit[™] HA monolithic femoral stem) will be computed at 5 years postoperative. For the non-inferiority comparison, the lower bound of this 90% confidence interval will be compared with -5%. If it is greater than -5%, non-inferiority is supported. In addition, if it is greater than 0%, superiority is supported. The Kaplan-Meier survival curve will also be displayed using SAS/PROC LIFETEST.

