9.2.2 Safety Analysis

All AEs will be listed, tabulated and summarized by event, number and percent of cases/subjects. AE rates and 95% confidence intervals will be presented. In addition, a

CONFIDENTIAL

Fisher's exact test will be used to compare the AE rates between the Rejuvenate® Modular Hip System and the Secur-Fit™ HA groups or cohorts, if appropriate.

For categorical variables, such as radiographic stability, the number and percent in each category will be presented.

9.3 *Missing Data*

No missing data will be imputed for the primary analysis and secondary analyses.

9.4 *Statistical Methodology*

9.4.1 *Data Summary*

The following is a detailed proposal of statistical analyses planned for data collected during the study.

Descriptive statistics will be computed for all preoperative conditions and demographic parameters. That is, for continuous data (e.g. HHS) the N, mean, median, standard deviation, minimum and maximum will be computed. For categorical data (e.g. gender) the frequency will be computed. If appropriate, the data will be presented by the Rejuvenate® Modular Hip System and the Secur-Fit™ HA groups.

Descriptive statistics and statistical comparisons for important demographic, efficacy and safety variables will be provided in tables.

A survival analysis for revision/removal of the modular femoral stem/neck construct will be performed.

9.4.2 *Sample Size Calculation*

Given an estimated revision rate for both groups at 2.5% and a non-inferiority margin of 5%, with a one-sided alpha of 0.05 and 80% power, a total of 147 cases per group are required to reject the null hypothesis that the revision rate for Rejuvenate® Modular Hip System cases is 5% greater than for Secur-Fit™ HA monolithic femoral stem cases. In order to control for a 20% drop-out rate, 183 cases per group are required.

CONFIDENTIAL

A total of 240 cases received the Secur-Fit™ HA femoral stem in the Trident® X3® Polyethylene Insert Study, a historical control. Therefore, although only 183 cases are needed for statistical power, 240 cases will be enrolled in the Rejuvenate® Modular Hip System Outcomes Study.

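### The primary non-inferiority margin is 7% in the hypothesis (Section 9.1.3) but 5% in the decision rule, sample size and synopsis, so one result can both pass and fail

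*Combined protocol and SAP*

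**What the plan says.** Four places in the combined protocol and SAP set or use the margin for the primary comparison of success, meaning freedom from stem/neck construct revision or removal, at 5 years.

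- **Section 9.1.3, Primary Efficacy Hypothesis:** "A non-inferiority comparison with a one-sided alpha set at 0.05, power of 80% and delta of 7% will be performed". The 7% appears again where δ is defined beneath H0 and Ha.
- **Section 9.1.4, Primary Efficacy Analysis:** "the lower bound of this 90% confidence interval will be compared with -5%. If it is greater than -5%, non-inferiority is supported".
- **Study Synopsis, Statistical Methodology:** the lower 90% bound is again set against -5%.
- **Section 9.4.2, Sample Size Calculation:** the study is sized on "a non-inferiority margin of 5%, with a one-sided alpha of 0.05 and 80% power". The null hypothesis to be rejected there is that "the revision rate for Rejuvenate® Modular Hip System cases is 5% greater than for Secur-Fit™ HA monolithic femoral stem cases".

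Sections 9.1.3 and 9.4.2 give the same one-sided alpha and power, and a 90% two-sided interval corresponds to that alpha. No passage gives a reason for two margins or says which section takes precedence.

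**The concern.** A non-inferiority test is defined by its margin. With δ = 7% in the hypothesis and -5% in the decision rule, the rule does not test the hypothesis as written, and the sample size was not derived for that hypothesis.

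The primary conclusion could then depend on which paragraph is followed. This matters more here than in a randomized, masked trial. The study is non-randomized, Appendix G describes it as open-label, and the comparator is a historical group from another study. A margin fixed in advance is one of the few protections against choosing a threshold after the results are known. As the text stands, either margin could be cited as pre-specified.

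The margins also differ in what they exclude. If the control revision rate is the planned 2.5%, a 5% margin excludes a true study rate of 2.5% + 5% = 7.5% or more, which is 3 times control. A 7% margin excludes only 2.5% + 7% = 9.5% or more, which is 3.8 times control. These are boundaries for the true rate, not observed rates that would pass.

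**Working it through.** **Inputs from the plan.** Revision rate 2.5% in both groups, one-sided alpha 0.05, power 80%, 147 per group before drop-out and 183 after 20% drop-out (Section 9.4.2); 240 cases per group (Section 9.4.2); 90% interval at 5 years (Section 9.1.4).

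**Assumptions.** The plan does not name the interval method. The main figures use the unpooled (Wald) interval, with Newcombe as a check. Evaluable hips are 240 × 0.80 = 192 per group, with 240 as the no-loss case. Control revisions are set at about 2.5%: 5 of 192, or 6 of 240.

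**The plan's own sample size.** The simple non-inferiority formula is n = (1.645 + 0.842)² × 2 × 0.025 × 0.975 / margin².

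- Margin 5%: n = 120.6, so 121 per group.
- Margin 7%: n = 61.5, so 62 per group.

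Neither equals 147. At 5%, other variants give 158 (continuity-corrected) and 163 to 164 (restricted-null variance). An exact score-test search first reaches 80% power at 149. The plan names no method, so 147 cannot be traced with certainty. That is a separate matter: the 5% basis of Section 9.4.2 rests on its explicit wording, not on this formula.

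**Results on which the two margins disagree.** With revision proportions a (study) and b (control), the lower bound for the difference in success is (b − a) − 1.645 × √[a(1−a)/n + b(1−b)/n].

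Worked case, n = 192, 9 study and 5 control revisions: b − a = 0.0260 − 0.0469 = −0.0208; standard error 0.0191; 1.645 × 0.0191 = 0.0314; lower bound −5.22%.

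| n per group | Control revisions | Study revisions | Lower bound | Rule -5% | Rule -7% |
|---|---|---|---|---|---|
| 192 | 5 | 8 | -4.60% | pass | pass |
| 192 | 5 | 9 | -5.22% | fail | pass |
| 192 | 5 | 10 | -5.85% | fail | pass |
| 192 | 5 | 11 | -6.47% | fail | pass |
| 192 | 5 | 12 | -7.09% | fail | fail |
| 240 | 6 | 11 | -4.85% | pass | pass |
| 240 | 6 | 12 to 15 | -5.35% to -6.81% | fail | pass |
| 240 | 6 | 16 | -7.29% | fail | fail |

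At 192 per group the Newcombe interval splits at the same counts, 9 to 11 (-5.55% to -6.80%).

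**Chance of declaring non-inferiority.** Exact binomial enumeration, control revision rate 2.5%, unpooled interval:

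| n per group | True study revision rate | Pass at -5% | Pass at -7% | Rules disagree |
|---|---|---|---|---|
| 192 | 2.5% | 92.8% | 99.4% | about 7% |
| 192 | 5% | 39.3% | 74.1% | about 35% |
| 192 | 7.5% | 6.3% | 25.1% | about 19% |
| 240 | 2.5% | 95.9% | 99.9% | about 4% |
| 240 | 5% | 42.7% | 81.4% | about 39% |
| 240 | 7.5% | 5.8% | 28.4% | about 23% |

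With Newcombe at 192 per group and a true rate of 7.5%, the pass probabilities are 5.0% and 21.6%.

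**The case against.** The strongest reply is that the ambiguity is narrower than two competing tests. Section 9.1.3 states a hypothesis but gives no pass/fail rule for a confidence bound. The only such rule, in Section 9.1.4 and the synopsis, uses -5%, and the sample size agrees. An analyst following Section 9.1.4 would apply -5%, and the 7% may simply be a leftover. Nothing in the documents suggests that anyone intends to choose the margin late. Under the planning assumption of equal 2.5% rates, the two rules would disagree only about 4% to 7% of the time.

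Most of this is fair. It shows which figure is the outlier and that the disagreement is small if the devices perform alike. It does not remove the contradiction. Section 9.1.3 is where the hypothesis is formally set, it says a comparison at 7% will be performed, and it gives that value twice, so a single mistyped digit is unlikely. The planning assumption is also the case in which the margin matters least: at 5% against 2.5% the rules disagree 35% to 39% of the time.

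**Conclusion.** The concern holds and must be fixed. The primary margin is internally inconsistent: 7% in Section 9.1.3, and 5% in Section 9.1.4, Section 9.4.2 and the synopsis.

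At the 5-point deficit that the study was sized to exclude, reading the margin as 7% raises the chance of a non-inferiority claim from about 6% to about 25% at 192 per group, roughly four times. These sizes rest on the assumed evaluable numbers, a 2.5% control rate and the unpooled interval; Newcombe gives the same picture. The contradiction itself rests on no assumption.

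**What to change.** In Section 9.1.3, replace 7% with 5% in both places: the sentence on alpha and power, and the definition of δ. The hypothesis, decision rule, synopsis and sample size would then share one margin. The sponsor should confirm that 5% was intended, and the change should be dated before any 5-year comparison with the control group.

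If 7% was intended, Sections 9.1.4 and 9.4.2 and the synopsis must all change instead, with a justification for the wider margin.

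The cost is two wording edits and an amendment submitted to the EC/IRB, as Section 14 requires. No extra patients are needed, because the sample size section already uses 5%.

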9.1.4 Primary Efficacy Analysis

A case success is defined as no incidence of femoral stem/neck construct revision/removal. The 90% confidence interval around the difference in success rate (Rejuvenate[®] Modular Hip System – Secur-Fit[™] HA monolithic femoral stem) will be computed at 5 years postoperative. For the non-inferiority comparison, the lower bound of this 90% confidence interval will be compared with -5%. If it is greater than -5%, non-inferiority is supported. In addition, if it is greater than 0%, superiority is supported. The Kaplan-Meier survival curve will also be displayed using SAS/PROC LIFETEST.

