9.4.4 Patient Populations

Modified Intent-to-Treat (ITT) Population: The study population for analysis will include all subjects who receive the Rejuvenate® Modular Hip System or the Secur-Fit™ HA monolithic femoral stem. This does not include cases censored from analysis for a reason that may have a significant impact on outcome.

The primary and secondary efficacy analyses will be based on the per protocol population.

Per Protocol Population: The study population will include all subjects who receive the Rejuvenate® Modular Hip System or the Secur-Fit™ HA monolithic femoral stem. This does not include cases that have major protocol violations including the violation of entry criteria. In order for cases to be included in the per protocol population, the data required for analysis of a specific parameter must be present. Any data of secondary variables will be included, where possible.

The primary efficacy analyses and safety analysis will be based on the modified ITT population; the secondary efficacy analyses will be based on the per protocol population.

10 Study Procedures

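### Two primary populations are named and no rule covers an unrevised hip lost before 5 years, so the −5% non-inferiority verdict can flip near the margin

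*Combined protocol and SAP*

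**What the plan says.** All references are to the combined protocol and SAP.

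- **Population (9.4.4).** One sentence reads "The primary and secondary efficacy analyses will be based on the per protocol population". A later one in the same section reads "The primary efficacy analyses and safety analysis will be based on the modified ITT population".
- **Who is left out (9.4.4).** For per protocol: "In order for cases to be included in the per protocol population, the data required for analysis of a specific parameter must be present". For modified ITT, which otherwise takes every implanted case: "This does not include cases censored from analysis for a reason that may have a significant impact on outcome". The plan does not define which reasons qualify.
- **Endpoint (9.1.4).** "A case success is defined as no incidence of femoral stem/neck construct revision/removal". The lower 90% limit of the difference in success rate at 5 years is compared with −5%, and a Kaplan-Meier curve is shown in addition.
- **Missing data (9.3).** "No missing data will be imputed for the primary analysis and secondary analyses".
- **Survival analysis (9.4.1).** "A survival analysis for revision/removal of the modular femoral stem/neck construct will be performed". It is not tied to the −5% test.
- **Planned loss (9.4.2).** "In order to control for a 20% drop-out rate, 183 cases per group are required". Each group has 240 cases.
- **Related text.** Section 11.6 lists an unavailable primary endpoint as a visit deviation, without saying whether it is a major violation. Section 10.3 lists death and loss to follow-up as separate termination reasons and dates a loss by the sponsor's approval to terminate.

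**The concern.** The two sentences in 9.4.4 cannot both hold, and they treat a lost hip differently. Under per protocol, an unrevised hip without 5-year status leaves the denominator, while revisions seen earlier stay in the numerator. Under modified ITT, a lost hip that is not removed as censored has no recorded revision and fits the success definition. The ban on imputation does not exclude that reading, because no value is filled in.

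Naming one population is therefore necessary but not enough: if modified ITT were kept, the lost-hip rule would still be open. With a fifth of the hips expected to be lost, the denominator could be chosen after the revision counts are known.

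**Working it through.** **Inputs.** From the plan: 240 per group, 20% drop-out, one-sided alpha 0.05, −5% rule, planning revision rate 2.5% (9.1.4, 9.4.2). Assumed: revision counts, loss timing, the control's loss and the interval method, since 9.1.4 names none. Both Wald and Newcombe limits are shown.

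**The plan's own figure.** 147 / 0.80 = 183.75, which the plan gives as 183. The inflation reproduces apart from rounding down. The 147 itself is a separate matter and is not used here. With 240 enrolled and 20% lost, 48 hips are lost and 192 remain.

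**Formulas.** p is the success proportion, d = p₁ − p₂, z = 1.645.
- Wald: L = d − z·√[p₁(1−p₁)/n₁ + p₂(1−p₂)/n₂]
- Newcombe: L = d − √[(p₁−l₁)² + (u₂−p₂)²], where l₁ and u₂ are 90% Wilson limits

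**Same data, two verdicts: 9 versus 4 revisions, 48 unrevised losses in each group.**
- Losses as successes (240/240): d = 0.9625 − 0.9833 = −0.0208. Wald −0.0208 − 1.645 × 0.01479 = **−4.5%**. Newcombe, l₁ = 0.9366 and u₂ = 0.9925: −0.0208 − 0.0274 = **−4.8%**. Pass.
- Losses excluded (192/192): d = 0.9531 − 0.9792 = −0.0260. Wald −0.0260 − 1.645 × 0.01841 = **−5.6%**. Newcombe, l₁ = 0.9211 and u₂ = 0.9906: −0.0260 − 0.0340 = **−6.0%**. Fail.

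On 240 versus 192, one or two study counts flip in this way for each control count from 0 to 8, by either method. At the planned rates (6 versus 6) both readings pass: Wald −2.3% and −2.9%.

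**False non-inferiority at a true 7.5% versus 2.5%, constant hazards, 20% loss in both groups.** Over 5 years the revision hazard is r = −ln(1−rate) and the loss hazard is ℓ = −ln(0.8) = 0.223. The share of hips with a revision seen is r/(r+ℓ) × [1 − e^−(r+ℓ)].
- Study: 0.0780/0.3011 × 0.260 = 6.73%. Control: 0.0253/0.2485 × 0.220 = 2.24%.
- Losses as successes: the expected difference shrinks to 6.73 − 2.24 = 4.49 points.
- Losses excluded: 6.73/0.807 = 8.34% and 2.24/0.802 = 2.79%, so the difference grows to 5.55 points.

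Exact binomial probability that the lower bound exceeds −5%:

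| Reading | Newcombe | Wald |
|---|---|---|
| No loss | 5.1% | 5.9% |
| Losses as successes | 8.4% | 9.7% |
| Losses excluded | 2.9% | 3.9% |

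Power with losses excluded, at 2.5% in both groups, is 86.5% (Newcombe) or 90.8% (Wald), above the 80% target.

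**Unequal loss: 5% study, 35% control (assumed).** The same formula gives 7.31% and 2.03% with losses as successes (5.28 points). Excluded, it gives 7.68% and 3.11% (4.57 points). Excluding losses now understates the true 5-point gap, and its error is about 8.6–8.7%.

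Example: 12 versus 6 revisions with 12 and 84 unrevised losses.
- On 240/240: d = −0.0250, Newcombe −0.0250 − 0.0310 = **−5.6%**. Fail.
- On 228/156: d = −0.0142, Newcombe −0.0142 − 0.0352 = **−4.9%**. Pass.

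**The case against.** The plan leans towards excluding lost hips. Sections 2.1.1 and 9.1.4 tie success and the interval to 5 years, 11.6 recognises that the primary endpoint can be unavailable, and 9.3 bars imputation. Above all, inflating 147 to 183 makes sense only if lost hips leave the analysed set. On that reading the rule is merely unstated, and the 8–10% error belongs to the less supported reading. Flips also occur only near the margin: 9 versus 4 passes on both counts against the 7% margin of 9.1.3.

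The lean is real, but it does not settle the matter. A sample-size allowance is not an analysis rule, and 9.4.4 still contains a sentence making modified ITT primary, with an undefined exclusion. The locality of the flip limits the size of the concern and not its validity.

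A reader might infer that counting losses as successes is always the lenient choice and that excluding them is always safe. The documents do not support this. It follows from equal loss in the two groups, and they do not report the historical control's loss.

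**Conclusion.** The point stands and should be settled before the 5-year analysis. Section 9.4.4 contradicts itself on the primary population, and no rule says how an unrevised lost hip enters the −5% comparison. The contradiction is a matter of text and rests on no assumption.

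The size does rest on assumptions. Under equal 20% constant-hazard loss, the error at the margin is about 8–10% with losses as successes and 3–4% with them excluded. The two readings give different verdicts in about 7–9.5% of trials at the planned equal rates and in about 20% at a true 5% versus 2.5%. Under unequal loss the ordering can reverse, so neither crude denominator is safe by default against a historical control.

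The text does not show that the sponsor intends to count lost hips as successes, and this point does not claim it. The figures use the 5% margin of 9.1.4 and 9.4.2; the 7% in 9.1.3 is a separate conflict to reconcile.

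**What to change.** 1. In 9.4.4 keep one primary population, and define or delete the clause on censored cases.
2. State, for both groups, that an unrevised hip without 5-year status is not counted as a success.
3. Base the −5% comparison on the difference in 5-year Kaplan-Meier revision-free probability, with a named interval. The choice matters: in simulation at 7.5% versus 2.5% with 20% loss, combined log-log limits gave an error a little under 5% and plain Greenwood limits a little over 6%. Censor unrevised lost hips at the last contact with the implant confirmed in place, and not at the termination-approval date of 10.3. State how deaths are handled. Use a crude known-status proportion as a sensitivity analysis, or as primary only if loss is shown to be similar in the two groups.
4. Report loss by group and a tipping-point analysis for lost hips.

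**Cost.** For the study group this is mainly SAP wording, since a survival analysis is already planned. The Study Termination CRF in Appendix F asks whether the device was in place at last contact but shows no field for that date, so it must come from visit records. Last-contact dates and implant status in the historical control must be confirmed as available; the documents do not show this. Kaplan-Meier is biased if loss is related to revision risk, which is why the tipping-point analysis is needed.
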